## 2.2.1 Preclinical Data

In this section a short summary of preclinical data is provided. More detailed information is presented in the selinexor Investigator's Brochure (Appendix C).

### 2.2.1.1 Pharmacology, Pharmacokinetic and Toxicology Summary:

Selinexor has shown potent apoptosis induction with a median IC50 of 90 nM across a panel of 46 tumor cell lines representing a broad spectrum of tumor types. As noted above, selinexor had little effect on normal lymphocytes or other non-transformed cells, which correlated with the low incidence in animals of the typical side effects seen with most anti-cancer therapies, such as significant myelosuppression, alopecia, mucositis and other gastrointestinal dysfunction. Selinexor has shown substantial efficacy, with dosing regimens that match those currently under investigation in humans, in a variety of mouse models of hematological and solid tumors and, including AML, CLL, DLBCL, MCL, multiple myeloma, T-cell acute lymphoblastic leukemia (T-ALL), neuroblastoma, melanoma and prostate, breast, lung and ovarian cancer.

AML cells overexpress the nuclear exporter, Exportin 1 (XPO1/CRM1) and higher XPO1 levels correlate with poor outcome (Kojima 2013). The novel selective inhibitor of nuclear transport / SINE compound, selinexor, antagonizes XPO1 and shows potent cytotoxicity for AML and ALL cells *in vitro*, independent of genotype.

Selinexor shows potent antiproliferative effect and induced apoptosis, cell cycle arrest and myeloid differentiation in AML cell lines and patient blasts, including those from patients with *NPM1* and *FLT3*-ITD mutations (Ranganathan 2012).

Mechanistic studies show that SINE compounds induce nuclear localization and activation of multiple tumor suppressor proteins (TSPs), leading to rapid apoptosis of AML cells. In addition, a strong down-regulation of the oncogenes *FLT3* and *c-KIT* were observed after SINE treatment in both *FLT3*-ITD and wild-type cell lines (Ranganathan 2012). Selinexor treatment also restored the localization of cytoplasmic mutant *NPM1* into the nucleus.

In murine AML and ALL models, selinexor showed potent antileukemic activity without toxicity to normal hematopoietic cells (Etchin 2013a, b; Ranganathan 2012).

*In vitro* experiments with continuous (~72 hour) exposure to selinexor demonstrated potent proapoptotic activity across a broad panel of tumor-derived cell lines and patient samples in culture including multiply resistant cancers, with the majority of inhibitory concentrations, 50% (IC50s) for cytotoxicity < 800 nM and most hematologic tumor lines having IC50s of 20-400 nM for selinexor. Moreover, selinexor demonstrated cytotoxicity in multiple myeloma (MM) and chronic lymphocytic leukemia (CLL) cells in the absence or presence of bone marrow stroma cells (BMSC). In contrast, normal cells typically underwent (or remained in) cell cycle arrest but were resistant to apoptosis-induction; cytotoxicity IC50s were typically > 5 μM. As noted above, selinexor had little effect on normal (non-malignant) lymphocytes or other nontransformed cells, which correlated with the low incidence in animals of the typical side effects seen with most anti-cancer therapies such as significant myelosuppression, alopecia, mucositis and other gastrointestinal (GI) dysfunction.

Preclinical parameters were assessed in three species: mouse (CD1), rat (Sprague-Dawley), and monkey (cynomolgus). While pharmacokinetic (PK) studies were limited to male animals for all three species, toxicokinetic (TK) evaluations were conducted in both sexes for rats and monkeys as part of the selinexor toxicology studies, and no consistent sex-related differences were observed in either species. No accumulation was observed in any of the multi-dose toxicology studies with an every other day dosing regimen for selinexor. Overall, systemic exposure was generally dose-proportional in all TK studies that involved multiple dose levels. Higher maximum concentration (Cmax) and earlier time to maximum concentration (Tmax) values were observed in monkeys that were fasted versus fed prior to dosing. Systemic exposure (area under the curve from first to last plasma measurement, AUClast) to selinexor achieved with gelatin capsules was comparable to that achieved with oral suspension dosing, with lower Cmax and later Tmax values observed with capsules, and was not affected by the feeding status in monkeys. Oral bioavailability (F%) of selinexor was remarkably consistent among the three species, with average values of 66.5%, 61.2%, and 67.5% in mice, rats, and monkeys, respectively.

Nonclinical toxicology studies indicated that the major side effects (dose limiting toxicities, DLTs) across all species are reduced appetite with anorexia-induced weight loss partially consistent with satiety induction. High calorie foods and glucocorticoids can mitigate weight loss in animals taking SINE XPO1 inhibitors.

See the selinexor Investigator's Brochure for more information (Appendix C).

### **2.2.2. Clinical Experience**

KCP-330-001: A Phase I Study of the Safety, Pharmacokinetics and Pharmacodynamics of Escalating Doses of the Selective Inhibitor of Nuclear Export (SINE) KPT-330 in Patients with Advanced Hematological Malignancies  
*Study Design:* This is a Phase-1, open-label, parallel-group study, with dose escalation and expansion phases, to determine the MTD, preliminary safety,

preliminary response, and PK of various selinexor dose schedules (3 to 85 mg/m^2 dosed 1-3 times weekly) in patients with RR hematologic malignancies, including:

- \_Chronic hematological malignancies (B-cell) – Multiple myeloma (MM), Waldenström’s Macroglobulinemia (WM), Non-Hodgkin’s Lymphoma (NHL), chronic lymphocytic leukemia (CLL)
- \_Acute Myeloid Leukemia (AML) - Any subtype except M4 (Acute Promyelocytic Leukemia [APL])
- \_Peripheral (PTCL) and Cutaneous (CTCL) T-Cell Lymphoma
- \_Acute Lymphoblastic Leukemia (ALL) - B- or T-cell
- \_Chronic Myelocytic Leukemia (CML)

This study is registered on ClinTrials.gov at NCT01607892.

Preliminary, unaudited response data (as of 04 Dec 2014) and safety reports (as of 01 Feb 2015) for AML patients are included in the attached IB v4.0\_03 April 2015 (Appendix C).

*Study Design:* Sixty-five heavily pretreated patients with progressive RR AML, most with  $\geq$  3 prior lines of treatment, were enrolled in the KCP-330-001 AML treatment arm and received selinexor 16.8-70 mg/m^2 in four-week cycles.

*Preliminary Response Results:* Among 63 evaluable patients, the CR rate, with or without full hematologic recovery, was 11%, ORR was 16%, and DCR was 49%. (Note: 16 patients [25%] were non-evaluable but were included in the AML response rate calculation, based on the ITT approach.) Best response results in AML patients as of 13 May 2014 are shown in Table 1. Patients could be deemed non evaluable due to either lack of post-dosing bone marrow assessments, failure to take the required number of doses of study medication, withdrawal of consent, or death during Cycle 1 prior to response determination. During this study, sixteen patients died during Cycle 1, including patients who were evaluable due to PD prior to death.

Table 1 Best responses in AML patients as of May 13. 2014

N	DCR	ORR	CR	CR(i/p)	PR	MLFS	SD	PD	NE
63	31	10	5	2	1	2	21	16	16
(100%)	(49%)	(16%)	(8%)	(3%)	(2%)	(3%)	(33%)	(25%)	(25%)

*Preliminary Safety Results:* Grade 3/4 TEAEs that were reported in > 3 patients include: fatigue (18%), and nausea (8%). Grade 3/4 thrombocytopenia (15%) and neutropenia (11%) were observed, however a majority of patients enrolled with baseline high-grade thrombocytopenia and neutropenia as part of progressive disease (which is associated with reduced hematopoietic function). The most

common Grade 1/2 TEAEs were diarrhea (82%), anorexia (78%), nausea (74%), and fatigue (65%). No DLTs were reported during the dose escalation phase, however due to SAEs that were seen at 85 mg/m^2 in study KCP-330-002, a maximum allowable dose of 70 mg/m^2 twice weekly was assigned for this and future studies. The anticipated selinexor dose for patients in future AML studies will be 80-100 mg (35-60 mg/m^2) twice weekly. For details of overall safety results in the AML patients and in all hematologic clinical studies please see the attached IB (Appendix C)

### **Potential Risks**

Selinexor is currently in clinical development and has not been approved by the Food and Drug Administration (FDA) for commercial use. Human experience with selinexor is currently limited and the entire safety profile is not known at this time. Measures will be taken to ensure the safety of the patients participating in this trial, including the use of stringent inclusion and exclusion criteria and close monitoring. Toxicity grading will be performed in accordance with National Cancer Institute (NCI) Common Terminology Criteria for Adverse Events (CTCAE) V4.03. If more than one different type of toxicity occurs concurrently, the most severe grade will determine the modification.

If toxicities are encountered, adjustments will be made to the study treatment as detailed in the sections below. All AEs and serious adverse events (SAEs) will be recorded during the trial and for up to 30 days after the last dose of study treatment or until the initiation of another anti-cancer therapy, whichever occurs first.

Side effects observed to date in patients are shown below. Please see Selinexor for Oral Administration Investigator's Brochure (Appendix C) for most up-to-date information.

#### **Most common side effects:**

- nausea
- loss of appetite
- fatigue
- vomiting
- weight loss
- diarrhea

#### **Less common:**

- change in taste
- changes in vision including blurred vision
- low platelets
- decrease in red blood cells
- low sodium without symptoms

### **Reproductive risks**

Patients should not become pregnant or father a baby while on this study because the drugs in this study can affect an unborn baby. Women should not breastfeed a baby while on this study. It is important patients understand the need to use birth control while on this study. It is not anticipated that female patients enrolling in this study will be able to conceive. However, in the rare event that this is possible, female patients of child-bearing potential must agree to use dual methods of contraception and have a negative serum pregnancy test at screening, and male patients must use an effective barrier method of contraception if sexually active with a female of child-bearing potential. Acceptable methods of contraception are condoms with contraceptive foam, oral, implantable or injectable contraceptives, contraceptive patch, intrauterine device, diaphragm with spermicidal gel, or a sexual partner who is surgically sterilized or post-menopausal. For both male and female patients, effective methods of contraception must be used throughout the study and for three months following the last dose.

**2.2.3** For further details of selinexor and sorafenib preclinical studies, clinical studies, toxicities, pharmacokinetics, and adverse events please see the selinexor Investigator Brochure (Appendix C) and sorafenib drug label (Appendix D).

### **2.3 Rationale for study:**

FLT3 inhibitors demonstrate potent anti-leukemic activity and improve outcomes in patients with relapsed/refractory AML and *FLT3-ITD* mutations. About 40-50% of such patients achieve marrow responses to FLT3 inhibitors, with 20-30% bridged to allogeneic stem cell transplant. Responses to *FLT3* inhibitors are usually maintained for 3-6 months but invariably these responses are transient (except among patients who undergo transplantation) due to the emergence of resistance. The causes of resistance include the acquisition of point mutations in the *FLT3* KD and non-mutational mechanisms of resistance include up-regulation of compensatory pathways including the *PI3K/Akt/mTOR*, *FOXO3A*, *SYK*, *RAS* and *STAT5/PIM* pathways, up-regulation of the *FLT3* ligand or receptor, mutations in other kinases (e.g. *CBL*), activation of anti-apoptotic proteins *BCL2*, *MCL1* and *BCL-x(L)*, and tumor microenvironment mediated resistance.

Selinexor is a first in class Selective Inhibitor of Nuclear Export / SINETM compound that specifically binds and inactivates XPO1, thereby forcing the nuclear retention of key TSP/GRP implicated in non-mutational resistance to FLT3-inhibitors including *AKT*,

*PI3K, mTOR, FOXO, STAT5, BCL2, BCL-x(L)*. Nuclear retention of these known mediators of non-mutational resistance may improve the efficacy and duration of response to FLT3 inhibitor sorafenib. Furthermore, Garzon et al identified a direct inhibition of FLT3 protein expression in AML samples after XPO1 inhibition. The indirect and direct impact of XPO1 inhibition on the FLT3 pathway support combining a XPO1 inhibitor (selinexor) with a FLT3 inhibitor (sorafenib). We have preclinical data recently generated showing activity of the KPT330+sorafenib combination in patients with D835 alone, double mutant D835+ITD and D842+ITD (Zhang et al., ASH poster, December 2015 – attached as appendix K). Based on this data we will evaluate in addition to FLT3-ITD also double mutant ITD+D835 as well as D835 alone FLT3 mutated patients. We do not have active therapies for D835 alone or double mutant AML patients and the preclinical data suggests this therapy may be active. In this initial trial, we propose to investigate whether selinexor in combination with sorafenib improves the response rates in patients with FLT3-ITD and –D835 mutated relapsed/refractory AML. If the combination proves to be well tolerated and results in improved response rates, we would expand the use of this approach in the frontline setting for FLT3-ITD and –D835 mutated AML.

### 3.0 STUDY DESIGN:

#### 3.1 General

The study will be a phase I/II, single-institution, open-label, non-randomized, parallel group clinical trial. The phase II will include two separate cohorts to be enrolled simultaneously. All patients will be registered through CORE/PDMS.

- **Phase I**
  - This will include FLT3-ITD and –D835 mutated patients with relapsed/refractory AML, including patients who may have been previously exposed to one or more FLT3-inhibitors. Relapsed/refractory status defined by the failure of at least one prior cycle of chemotherapy (including but not limited to cytotoxic chemotherapy, hypomethylator therapy, immune-based therapy, stem cell transplant or stem cell therapy, FLT3-inhibitor therapy, investigational therapy, and others).
  - The DLT assessment period will be performed only during Cycle 1 of Phase I.
  
- **Phase II in two cohorts**
  1. **Cohort 1 (FLT3 inhibitor failure cohort)** in FLT3-ITD and –D835 mutated relapsed/refractory AML who have failed therapy with up to two prior salvage regimens (HSCT or stem cell therapy for patients who previously underwent HSCT/stem cell therapy in remission will not be considered a salvage regimen) and have previously been exposed to at least one prior FLT3 inhibitor.

2. **Cohort 2 (FLT3 inhibitor naive cohort)** in FLT3-ITD and –D835 mutated relapsed/refractory AML who have failed therapy with up to two prior salvage regimens (HSCT or stem cell therapy for patients who previously underwent HSCT/stem cell therapy in remission will not be considered a salvage regimen) with no prior exposure to any FLT3 inhibitor.

### 3.2 Study Design

- The phase I portion is aimed at finding the MTD and RP2D of the combination drugs. We will use the standard “3+3” design. The target dose is dose level +1, and the starting dose will be dose level 0. The first 3 patients on study will receive dose level 0.
- Other dose levels will be used for dose adjustments for toxicity during therapy (Table 3).
- Prior to advancing/changing dose levels, a cohort summary will be completed and submitted to the IND Office Medical Monitor for review and approval. A copy of the cohort summary should be placed in the Investigator’s Regulatory Binder under “sponsor correspondence”.
- The dosing schema is shown in Table 3 below.

**Table 3: Dosing schema**

Dose level	Sorafenib (in mg)	Selinexor (in mg) on days 1 and 3 of weeks 1-3 of each 4 week cycle
+1 (Target dose)	400 twice daily	100 mg* twice weekly
0 (Starting dose)	400 twice daily	80 mg twice weekly
-1	400 twice daily	60 mg twice weekly
-2	400 twice daily	40 mg twice weekly

\*not to exceed 70 mg/m^2 based on BSA

### 3.3 3+3 algorithm

The 3+3 algorithm that we will follow in the phase I is described below.

- Enroll 3 patients at the dose level 0
- Proceed to the next higher dose level with a cohort of 3 patients until at least 1 patient experiences the dose-limiting toxicity (DLT)
- If only 1 of 3 patients experiences the DLT at a given dose level, enter 3 additional patients at the current dose level
- If only 1 of 6 patients experiences the DLT at a given dose level, proceed to the next higher dose level with a cohort of 3 patients or open broadly for phase II if at maximum escalation dose
- If at least 2 of 3 or 2 of 6 patients experience the DLT at a given dose level, then the MTD has been exceeded
- Once the MTD has been exceeded, treat another 3 patients at the previous dose level if there were only 3 patients treated at that dose level

- The MTD is the highest dose level in which we have treated 6 patients with at most 1 experiencing the DLT
- If  $\geq 2/6$  patients experience DLT at dose level -2, the study will be revised to consider additional lower dose levels.

\*With up to 2 potential dose de-escalation level (-1 and -2) to be studied and up to 6 patients to be treated at a given dose, the target maximum number of patients enrolled in the phase I part of the trial will be 12.

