## 11.0 STATISTICAL CONSIDERATIONS

The primary objectives of the study are to evaluate safety and efficacy of selinexor in combination with sorafenib in patients with FLT3-ITD and -D835 mutated AML. The total accrual is 52 patients (Phase I: up to 12 patients and Phase II: 20 patients per cohort).

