### 11.1 Phase I

In order to determine the MTD of selinexor in combination with sorafenib, we will use the standard 3+3 design for dose finding. The MTD is defined as the highest dose level with  $\leq 1$  out of 6 patients experience a DLT during the first 28 days of treatment. **DLT is defined in section 3.4 (page 13)**. The 3+3-dosing algorithm is presented in section 3.3 and the dosing schema for the combination treatment is shown in Table 3. The RP2D will be selected at the end of the phase I portion based on safety and efficacy of selinexor and sorafenib after discussion with the sponsor and the supporting company (Karyopharm). The Investigator is responsible for completing the cohort summary template prior to advancing subjects to the phase II part. Once RP2D has been established, any patients

still on study at a dose lower than RP2D can be dose escalated up to RP2D in accordance with the dose-escalation guidelines in section 5.2.3.

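### The Phase I maximum of 12 counts only levels -1 and -2 and omits level 0 (and +1); if the lower levels are dose-finding levels, the maximum is 24 and the total up to 64, not 52

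*Combined protocol and SAP*

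**What the plan says.** The footnote to the algorithm in section 3.3 gives both the figure and its derivation. Its premise is "With up to 2 potential dose de-escalation level (-1 and -2) to be studied and up to 6 patients to be treated" at any one dose, and its conclusion is that "the target maximum number of patients enrolled in the phase I part of the trial will be 12". Section 11.0 repeats the figure without the word target: "The total accrual is 52 patients (Phase I: up to 12 patients and Phase II: 20 patients per cohort").

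The rest of the design bears on whether 12 can be a maximum:

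- Sections 3.2 and 3.3 put the first three patients at level 0 and name +1 as the target level. Table 3 lists four levels: +1, 0, -1 and -2.
- A level goes to six after one DLT in three patients, and is exceeded at two DLTs in three or in six.
- After a level is exceeded, the rule is to "treat another 3 patients at the previous dose level if there were only 3 patients treated at that dose level".
- Declaring an MTD needs a full six at that level, by this definition: "The MTD is the highest dose level in which we have treated 6 patients with at most 1 experiencing the DLT".
- For two or more DLTs in six, section 3.3 has a rule for the lowest level: "DLT at dose level -2, the study will be revised to consider additional lower dose levels".
- Section 11.1 ties the rule to the full table: "The 3+3-dosing algorithm is presented in section 3.3 and the dosing schema for the combination treatment is shown in Table 3".
- Section 5.2.2 provides for an MTD below level 0, and section 5.4.4 lists the selinexor doses of levels -1 and -2 as possible de-escalation doses.
- Section 3.2, after naming levels 0 and +1, says: "Other dose levels will be used for dose adjustments for toxicity during therapy".
- Sections 3.4 and 5.1.1.5 require patients who cannot be evaluated for DLT to be replaced.

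**The concern.** The 12 is the product of two levels and six patients, and the two levels named are the ones that can be reached only after another level has failed. The patients at level 0 are therefore missing from the count, as are any at +1. A maximum that leaves out the starting cohort cannot bound the trial on the footnote's own premise.

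What is at stake is the stated size of Phase I and the accrual ceiling of 52. If the combination proves more toxic than hoped, the study could reach its declared Phase I limit partway through de-escalation, before an MTD is established, and need an amendment at that point. The dose-finding rule itself, and everything in Phase II, does not depend on the number.

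**Working it through.** **Reproducing the plan's figures.** Levels -1 and -2 at six each: 2 × 6 = 12. Phase I plus two cohorts of 20: 12 + 20 + 20 = 52. Both match the text.

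**Inputs.** From 3.2, 3.3 and Table 3: start at level 0 with three patients; cohorts of three; at most six per level; six patients with at most one DLT to declare the MTD; four levels. Two steps are not written in 3.3 and are assumed here. An untreated lower level opens with three patients when the level above is exceeded. A result of 0 of 3 at +1 is expanded to six, because the MTD requires six. All patients are taken as evaluable.

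**Counts when -1 and -2 are both filled to six, as the footnote supposes.** These need no DLT rates.

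| Path | Level 0 | +1 | -1 | -2 | Phase I |
|---|---|---|---|---|---|
| Level 0 exceeded in its first three | 3 | 0 | 6 | 6 | 15 |
| Level 0 exceeded at six | 6 | 0 | 6 | 6 | 18 |
| 0 of 3 at level 0; +1 exceeded in three; level 0 then exceeded at six | 3 + 3 | 3 | 6 | 6 | 21 |
| As above, but +1 exceeded at six | 3 + 3 | 6 | 6 | 6 | 24 |

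The largest value is four levels × 6 = 24, giving a total of 24 + 40 = 64. If +1 is never opened it is 3 × 6 = 18, giving 18 + 40 = 58. Replacements are extra.

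**Where 12 does hold.** Levels 0 and +1 alone cannot exceed 6 + 6 = 12. Some downward paths also end at 12, for example 3 at level 0, 3 at -1 and 6 at -2. Over all paths the possible sizes are 9, 12, 15, 18, 21 and 24, and every path above 12 includes level -1.

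**How often 12 is exceeded.** The documents give no DLT rates, so the rates below are assumptions. At each cohort of three the chance of *k* DLTs is C(3,k) p^k (1−p)^(3−k). Multiplying along each path and summing over all paths gives exact results.

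| Assumed DLT rate at -2 / -1 / 0 / +1 | P(n > 12) | P(n = 24) | Mean n |
|---|---|---|---|
| 2 / 5 / 10 / 15% | 0.007 | 0.0001 | 10.1 |
| 10% at all levels | 0.012 | 0.0001 | 10.0 |
| 5 / 10 / 20 / 30% | 0.061 | 0.002 | 11.0 |
| 10 / 20 / 30 / 40% | 0.206 | 0.007 | 11.9 |
| 15 / 25 / 35 / 50% | 0.298 | 0.009 | 12.4 |
| 20 / 30 / 40 / 50% | 0.371 | 0.010 | 12.8 |

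**Sensitivity to the two assumed steps.** If 0 of 3 at +1 ends Phase I, P(n > 12) runs from 0.007 to 0.367 over these scenarios. If a lower level opens with six at once, it runs from 0.008 to 0.468, and P(n = 24) is at most 0.017. The maximum is 24 in each variant.

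**The case against.** The strongest objection is that levels 0 and +1 at six each also give 12, and that 3.2 describes the other levels as serving dose adjustments during therapy. On that reading dose finding covers two levels and 12 evaluable patients is exactly right. No bullet in 3.3 opens an untreated lower level; the only downward step adds three at a level that already has three. This stands as a real ambiguity, and it limits certainty about which number should replace 12. It does not rescue the stated derivation, which names -1 and -2 as the levels to be studied and not 0 and +1. The DLT rule for level -2 and the text of 5.2.2 and 5.4.4 also point to de-escalation within dose finding.

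A reader might go further and infer that 3.2 and 3.3 flatly contradict each other. The documents do not support that: 3.2 does not say that the other levels are used only for adjustments.

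Second, 3.3 says target maximum, which is planning language, and 3.2 requires a cohort summary and Medical Monitor approval before any change of level, so 12 would not be passed unnoticed. Both points are fair. But 11.0 drops the qualifier, and a review step does not correct a number.

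Third, the practical effect is small in most settings. That is right. A reader might take 64 as the size to expect, or conclude that Phase I will usually overrun. Neither follows: 24 is a rare upper bound, and mean Phase I size stays between 10.0 and 12.8 in the scenarios examined.

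**Conclusion.** The concern holds, conditional on -1 and -2 being dose-finding levels. On the footnote's own premise, with both lower levels filled to six, Phase I takes at least 15 patients and cannot be 12. The maximum is 24 (18 if +1 is never opened) and the total up to 64 (58), against the stated 12 and 52, with replacements on top. These bounds rest on the inferred step down to an untreated level, but on no toxicity rates.

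How likely the excess is depends on assumed rates: 0.7% to 6.1% when the level 0 DLT rate is 20% or less, and 21% to 37% when it is 30% to 40%, with 24 itself reached in 1% of trials or fewer. The stated ceiling is therefore least dependable when the combination is more toxic than hoped.

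This is an error in the stated sample size and should be corrected. It does not touch the MTD criterion, the Phase II cohort sizes, the stopping boundaries or the operating characteristics.

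**What to change.** If -1 and -2 are dose-finding levels, restate 3.3 and 11.0 along these lines: *Phase I: up to 24 DLT-evaluable patients (four levels × 6), plus replacements for non-evaluable patients; Phase II: 40; total up to 64 plus replacements, excluding any lower levels added if level -2 fails.* Alternatively, keep 12 as a planning figure, call it a target in 11.0 as well as in 3.3, and print the maximum beside it.

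In either case, reconcile 3.2 with 3.3, 5.2.2 and 5.4.4 on the role of -1 and -2, and state in 3.3 what follows when a level is exceeded and the next lower one is untreated. If the sponsor limits dose finding to levels 0 and +1, then 12 evaluable patients is correct, and the de-escalation text must be reconciled with that. Which levels are studied is for the sponsor to decide.

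The cost is text edits in 3.2, 3.3 and 11.0 and, under the first option, a declared accrual ceiling higher by 12 patients (12 / 52, about 23%) plus replacements. The number of patients the dose-finding rule actually needs does not change.
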